This study will evaluate the changes in respiratory mechanics following TBI and determine the effect of inhaled nitric oxide on gas exchange.

4. Purpose of Study:

[figure not shown]
To determine the changes in respiratory mechanics in patients with traumatic brain injury (within 36 hours of admission and day 3 following admission).

To evaluate the effect of inhaled nitric oxide on gas exchange in patients with traumatic brain injury within 36 hours of admission.

Hypothesis: Inhaled nitric oxide improves oxygenation and reduces deadspace to tidal volume ratio following TBI.

5. Background:

Intubation and mechanical ventilation are common treatments in the care of patients with traumatic brain injury (TBI). Intubation allows for airway control and facilitates removal of respiratory secretions. Mechanical ventilation allows control of arterial carbon dioxide to aid in control of intracranial pressure. Recent evidence suggests that lung protective ventilation (tidal volumes of 6 ml/kg of predicted body weight and moderate positive end expiratory pressure) improves outcomes following brain injury and reduces brain-lung cross talk. Figure 1.

Respiratory failure following traumatic brain injury is a common complication resulting in hypoxemia and is associated with release of inflammatory mediators which may damage distal organs including the brain. The etiology of respiratory

failure following brain injury is multifactorial. Isolated head trauma is associated with neurogenic pulmonary edema and changes in ventilation perfusion matching. Concomitant trauma to the chest and pulmonary contusion may further worsen lung injury. It has been suggested that brain injury primes the lung to be a greater risk to a second hit (pneumonia, ventilator induced lung injury, lung contusion). Loss of consciousness can lead to aspiration of oral or gastric contents leading to pneumonia. Importantly, respiratory failure following TBI is implicated in 50% of deaths and prolonged ICU and hospital stay. (4,5)

The treatment of respiratory failure in TBI must balance the need to improve lung function with the negative consequences of increased intrathoracic pressure on mean arterial pressure, intracranial pressure and venous return. Traditional treatment of increasing PEEP and mean airway pressure then, represent competing interests. Methods for improving arterial oxygenation while avoiding negative hemodynamic effects are needed.

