5. Positive end expiratory pressure (PEEP) will be titrated from baseline PEEP as set at time of enrollment to 15 cm H_2O (in 5-cm H_2O increments) while measuring all the variables listed in #1-4 above. This method will determine the best PEEP and determine recruitability of the lung. FRC will be measured at three levels of PEEP from baseline to a maximum of 15 cm H_2O . This is an automated measurement requiring approximately 15 minutes to complete. If the patient develops hypotension (systolic pressure < 90 mm Hg or mean arterial pressure < 60 mm Hg) participation in the PEEP trial will be terminated.
6. Following these initial measurements, patients will be randomized to receive either a placebo (nitrogen and oxygen) or inhaled NO at 20 ppm for 2 hours \pm 30 minutes. After receiving the placebo or inhaled NO, the measurements in #1-4 will be reassessed (no change in PEEP will be made during this time unless required for clinical purposes).
7. If the patient remains on the ventilator at day 3 (72 hours after admission), 1-6 above will be repeated.

Subjects will receive placebo or drug for no more than 5 hours total.

If the patient responds to NO with a brisk increase in SpO₂ or PaO₂ – sudden withdrawal of NO can result in a fall in oxygenation (rebound pulmonary hypertension). This is uncommon in the absence of pulmonary hypertension. Prevention of rebound pulmonary hypertension is accomplished by increasing FIO₂ by 10-20% prior to discontinuation of NO, followed by a return to baseline FIO₂ over 30 mins.

If ICP goes up by >20% NO will be discontinued.

7. Research data collection/study procedures:

The patient baseline demographics including injury mechanism, severity and distribution, Glasgow coma scale score, age, gender, any witnessed aspiration, and lung mechanics measurements listed above will be collected to data sheets and then entered into a RedCap database. We will also record ventilator settings, lung compliance, airways resistance, dead space to tidal volume ratio, functional residual capacity, blood gases and duration of total mechanical ventilation, days in the ICU, hospital days and survival will be collected from the medical record and also entered into the RedCap database. See sequence of events for study measures.

8. Specimen collection:

The following blood samples will be taken:

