At baseline up to 3.5 ml will be taken. 1.5 ml for arterial blood gas testing (tests include: arterial pH, PaCO₂, PaO₂, SaO₂ and HCO₃) and 2 ml for measurement of inflammatory mediators specific to the lung.

After 90 to 120 minutes of nitric oxide/placebo delivery, less than 1.5 ml will be taken for arterial blood gas testing.

At the end of the study, up to 3.5 ml will be taken. 1.5 ml for arterial blood gas and 2 ml for measurement of inflammatory mediators specific to the lung.

The blood will be taken from indwelling lines when possible. If we are unable to obtain any of the blood samples, the subject will remain in the study and all other data will continue to be collected

9. Potential Benefits:

The detailed measurement of respiratory mechanics will be provided to the clinical team. This information which is not routinely measured can be used to optimize ventilator support beyond traditional monitoring. The determination of FRC and recruitability of the lung may assist the clinical team in identifying the best PEEP for each individual patient.

If the patient has a significant increase in PaO_2 associated with INO/placebo delivery, the clinical team can use that information to implement INO therapy as part of clinical care. It is unlikely that placebo will increase oxygenation appreciably. We will not unblind the study, the clinical team will have to make this decision based on a supposition of INO delivery.

Understanding the changes in respiratory function following TBI and the response to INO may improve treatment regimens for future patients.

10. Potential Risks, Discomforts, and inconveniences:

Level of risk: Greater than minimal risk.

The measurements to be made utilize non-invasive measures of lung volumes, flows, and pressures to determine mechanics.

Arterial puncture/venipuncture may cause pain/discomfort, bruising, fainting, and infection from phlebotomy sites.

Hypotension in severe pulmonary hypertension and left ventricular failure (very uncommon).

Methemoglobinemia has only been reported at 80ppm.

The stepwise increase in PEEP to determine changes in FRC will be limited to a maximum of 15 cm H_2O . PEEP can decrease venous return and cause transient hypotension. The risk of hemodynamic compromise at these low pressures is small. All subjects will have blood pressure and heart rate continuously monitored (as is standard of care) throughout the measurements.

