Research personnel will remain at the bedside throughout the measurements of respiratory mechanics which will require approximately 30 minutes to complete.

11. Data Safety monitoring plan and/or DSMB:

[name] will act as medical monitor for the study. He will review subjects' research data and adverse events to ensure patient safety. The medical

monitor will have the power to temporarily or permanently halt enrollment if it is deemed that patient safety is compromised.

12. Data Analysis:

Descriptive statistics will be employed to summarize relevant patient demographic factors as well as on baseline measurement of clinical variables. As a check on the success of randomization, these variables will be compared between groups using t-tests or chi-square tests, as appropriate.

The primary endpoint for this study is a change in $\text{PaO}_2:\text{FiO}_2$ ratio of 20 percent or greater between baseline and Day 3. The proportions of patients achieving success according to this criterion will be compared between groups using a two-sided z-test with pooled variance.

Group sample sizes of 19 in group one and 19 in group two achieve 82% power to detect a difference between the group proportions of 0.40. The proportion in group one (the treatment group) is assumed to be 0.10 under the null hypothesis and 0.50 under the alternative hypothesis. The proportion in group two (the control group) is 0.10. The test statistic used is the two-sided Z test with pooled variance. The significance level of the test was targeted at 0.05. The significance level actually achieved by this design is 0.0361.

Respiratory mechanics will be presented as descriptive (Mean, SD, range). Up to 43 subjects may be enrolled, in order to obtain the required 38 evaluable subjects. Patients will be removed from the study and its analysis if extubated by the clinical treatment team during the 72 hour NO protocol.

13. Data storage and confidentiality (include sample storage if applicable)

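### The nitric oxide objective concerns the first 36 hours, but the only efficacy test uses PaO2:FiO2 change to Day 3, and the session-1 blood gas is never analysed

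*Combined protocol and SAP*

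**What the plan says.** Section 4 (Purpose of Study) has two aims. The respiratory-mechanics aim names two times, the first 36 hours and day 3. The INO aim names one: "To evaluate the effect of inhaled nitric oxide on gas exchange in patients with traumatic brain injury within 36 hours of admission". Section 6 draws the same line, linking the 3-day period to mechanics.

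Section 6, item 6 randomises patients to placebo gas or INO for 2 hours ± 30 minutes in the first session. Item 7 then says: "If the patient remains on the ventilator at day 3 (72 hours after admission), 1-6 above will be repeated".

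Section 8 lists blood gases at baseline, during gas ("After 90 to 120 minutes of nitric oxide/placebo delivery, less than 1.5 ml will be taken for arterial blood gas testing") and at the close ("At the end of the study, up to 3.5 ml will be taken"). Section 7 points to a schedule ("See sequence of events for study measures") that is not in the text supplied.

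Section 9 says that after a marked rise in PaO2, "the clinical team can use that information to implement INO therapy as part of clinical care".

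Section 12 defines success as a change in the P/F "ratio of 20 percent or greater between baseline and Day 3" and compares the arms with a two-sided pooled z-test. The other planned analyses are baseline balance checks and a descriptive summary of mechanics. The section also states: "Patients will be removed from the study and its analysis if extubated by the clinical treatment team during the 72 hour NO protocol".

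**The concern.** The question and the test sit at different times. The objective asks whether INO changes gas exchange early after injury. The test asks whether P/F differs from baseline on Day 3. The blood gas that would answer the objective is drawn, but no analysis uses it. P/F is not among measurements 1 to 4 of section 6, so the descriptive summary of mechanics does not cover it either.

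Two consequences follow. A null Day 3 result would not show that INO lacks an early effect. A positive result would apply to patients still ventilated at 72 hours, not to the population and time in the objective. The removal rule adds to this by discarding completed session-1 data because of an event that happens after randomisation and after the session-1 response has been measured.

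**Working it through.** **1. The plan's own figure.** Inputs from section 12: 19 per arm, success 0.50 (INO) against 0.10 (control), two-sided pooled z-test, target alpha 0.05. I enumerated all outcomes (x, y), rejecting when |x/19 − y/19| / √[p̄(1 − p̄)(2/19)] exceeds 1.96, with p̄ = (x + y)/38. Rejection probability is 0.8154 at 0.50 against 0.10, and 0.0361 at 0.10 against 0.10. The stated values are 82% and 0.0361, so the calculation reproduces. The problem is the endpoint attached to it.

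**2. Timing.** The latest baseline is 36 h, so baseline to Day 3 spans at least 72 − 36 = 36 h (1.5 days) and at most about 3 days. Allowing an assumed 1 h for the initial measurements and the maximum 2.5 h of gas, session-1 gas ends by about 36 + 1 + 2.5 = 39.5 h. That leaves about 32 h or more before Day 3.

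**3. What each Day 3 sample would measure.**
- Pre-gas: only carry-over from about 2 hours of gas that ended some 32 hours or more earlier, plus the clinical course.
- On gas: a Day 3 response mixed with 1.5 to 3 days of clinical change, in ventilated patients only, possibly after clinical INO use.
- After the Day 3 gas has stopped: an uncertain residue of either. Section 6 also has FiO2 raised before withdrawal in responders and returned over 30 minutes. I have not modelled this case.

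None of these is the session-1 response.

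**4. Illustration of power.** The documents give no P/F variability, drift or carry-over. I assume that log P/F change is normal with control mean m and standard deviation SD, that INO multiplies P/F by 1.2, and that only increases count as success. Then:
- control success = P(Z > (ln 1.2 − m)/SD)
- INO success = P(Z > (ln 1.2 − m − f·ln 1.2)/SD)

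where ln 1.2 = 0.182, f = 1 on gas, and f = the carry-over fraction pre-gas. With m = 0, 10% control success requires SD = 0.182/1.2816 = 0.142. Rejection probability at 19 per arm, m = 0:

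| SD | Control success | On gas (f = 1) | Pre-gas, f = 0 | f = 0.25 | f = 0.5 |
|---|---|---|---|---|---|
| 0.142 | 10% | 0.815 | 0.036 | 0.086 | 0.247 |
| 0.20 | 18% | 0.583 | 0.049 | 0.076 | 0.171 |
| 0.30 | 27% | 0.327 | 0.051 | 0.068 | 0.119 |
| 0.40 | 32% | 0.210 | 0.055 | 0.066 | 0.095 |

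The 0.815 in the first row is calibration: these inputs force 50% against 10%.

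Drift matters too (on gas, f = 1). With m = −0.2, a 10% control rate implies SD = (0.182 + 0.2)/1.2816 = 0.298; INO success is then 25% and power 0.226. With m = +0.1, power is 0.869, 0.598, 0.319 and 0.203 at the four SDs, so one case beats the plan.

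**5. Removal rule.** Section 12 allows 43 − 38 = 5 losses (5/43 = 11.6%). At the planned rates, with assumed extubation by 72 hours:
- 20% (about 34 left, 17 per arm): power 0.750
- 30% (about 30 left, 15 per arm): 0.726
- 40% (about 26 left, 13 per arm): 0.658

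If all 43 had both session-1 samples, power would be 0.852 (22 INO, 21 control) or 0.859 (21 and 22), provided 0.50 and 0.10 apply to session 1.

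**The case against.** The strongest reply is that the 36 hours in the INO objective describes when patients are enrolled, not when the effect is measured. Section 15 makes anyone not enrolled by 36 hours a screen failure, and the hypothesis in section 4 names no time. Day 3 could then be the intended question: the gas is repeated then, the 5-hour cap on exposure equals two sessions of 2.5 hours, and section 12 speaks of a 72-hour protocol. This reading is possible. It is weakened by the companion aim, which names day 3 explicitly where the INO aim does not. Even if it is accepted, the objective needs rewording, the Day 3 sample needs defining, and the early response remains unanalysed.

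Three further points stand in part. The missing schedule may define the Day 3 sample, though it would not reconcile section 12 with section 4. The power figures rest on assumed inputs and say little about this trial's actual power. Section 12 also gives no direction for the change: under the same model with m = 0 and SD 0.142, counting 20% changes either way gives power of about 0.66 instead of 0.815.

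Finally, the hypothesis covers dead space as well. The descriptive summary may include it after session 1, but no comparison between arms is stated.

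**Conclusion.** The concern holds and should be fixed before the analysis is relied on. The mismatch between objective and tested endpoint follows from the text alone, with high confidence and no modelling. That the Day 3 sample is undefined holds for the text available, subject to the schedule that was not supplied.

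The effect on power cannot be fixed from the documents. The modelled figures show only that the stated 82% is secure for Day 3 if the 0.10 and 0.50 rates happen to hold there, and that plausible multi-day variability, drift or a pre-gas sample could take it far lower. The documents give no source for those rates. Section 9's remark that placebo is unlikely to raise oxygenation much suggests that a low control rate fits an acute response better than a multi-day change, but that is inference.

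**What to change.** **Primary endpoint.** Define success as a P/F increase of 20% or more from the session-1 pre-gas blood gas to the session-1 sample at 90 to 120 minutes. State the direction explicitly.

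**Sampling.** Draw the second sample while study gas is running and before any FiO2 change made for withdrawal; the ± 30 minutes in section 6 allows gas to end at 90 minutes. Record gas status, FiO2 and PEEP at both samples. The timing of mechanics and FRC in item 6 can stay as it is.

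**Analysis set.** Include every randomised patient with both session-1 samples, in the assigned arm. Report missing blood gases by arm. Apply the removal for extubation only to Day 3 analyses.

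**Secondary endpoints.** Keep baseline to Day 3, and add the Day 3 pre-gas to on-gas change. Say which Day 3 sample is used, and record any clinical INO use before it.

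**Alternative.** If Day 3 is the intended question, restate the section 4 objective to match and define the Day 3 sample.

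**Cost.** Wording for the endpoint and analysis set, plus one sampling instruction. Both session-1 blood gases are already scheduled and ventilator settings are already recorded. The 38 evaluable patients and the stated power carry over if 0.10 and 0.50 are restated, and justified, as session-1 rates. The price is that the Day 3 comparison becomes secondary.

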Mechanical ventilation following TBI is provided with the normal goals, reduce the work of breathing, provide adequate oxygenation, maintain normo- or hypocapnia and avoid lung injury. However, in an effort to improve brain tissue PaO_2 (TbO_2) mechanical ventilation in TBI may include increases in mean airway pressure and FIO_2 unrelated to the degree of lung dysfunction. Ventilatory support is always a balance of competing interests. Increases in airway pressure by increasing tidal volume, prolonging inspiratory time or increasing PEEP must be balanced against the risk of lung injury and hemodynamic interference. In TBI these must be furthered balanced against the impact on mean arterial pressure, cerebral perfusion pressure and venous return. (6)

Inhaled nitric oxide (INO) is a selective pulmonary vasodilator that at low doses (5-20 ppm) improves V/Q matching and at higher doses (80 ppm) reduces pulmonary artery pressures. Nitric oxide plays a role in a number of biologic processes and pathways that have been associated with improvements in brain function. (7,8) INO has been used in patients with TBI with successful increases in oxygenation in small case series. (10-11). These reports are not systematic applications of INO but rather rescue therapy in the face of ARDS.

The use of INO in ARDS has not proven to impact outcomes. (12-13) Several studies have shown improved gas exchange but no changes in morbidity or mortality. Despite these findings, INO is often used in ARDS to help improve gas exchange without increasing the risk of lung injury by increasing lung volumes or pressures.

This study will determine the etiology of lung dysfunction following TBI and describe the effect of INO on cardiorespiratory variables.

Inhaled nitric oxide (INOmax) is FDA approved and delivered via the INOmax DS_{IR} and FDA cleared delivery and monitoring device. The use of inhaled nitric oxide is limited to a maximum of 80 ppm. We will deliver 20 ppm, a dose that is widely prescribed.

6. Study design:

This study will determine the impact of inhaled nitric oxide on gas exchange and hemodynamics in a series of up to 43 patients with TBI over an 18 month period. The delivery of INO will be blinded. The study will also describe the changes in respiratory mechanics over a 3 day period.

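### Change in respiratory mechanics to Day 3 is the first stated purpose, but section 12 specifies no summary of within-patient change and no interval for it

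*Combined protocol and SAP*

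**What the plan says.** Section 4 (Purpose of Study) lists first: "To determine the changes in respiratory mechanics in patients with traumatic brain injury (within 36 hours of admission and day 3 following admission". Section 6 (Study design) puts the same aim in descriptive terms: "The study will also describe the changes in respiratory mechanics over a 3 day period".

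The design produces paired data. Section 6, item 7 states: "If the patient remains on the ventilator at day 3 (72 hours after admission), 1-6 above will be repeated". Each session therefore has pre-gas values of compliance, resistance, Vd/Vt and FRC (items 1 to 4), values along a PEEP titration (item 5), and values after the study gas (item 6).

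The whole analysis text for these measurements is one sentence in section 12 (Data Analysis): "Respiratory mechanics will be presented as descriptive (Mean, SD, range". The same paragraph sets the number of patients, "Up to 43 subjects may be enrolled, in order to obtain the required 38 evaluable subjects", and a removal rule, "Patients will be removed from the study and its analysis if extubated by the clinical treatment team during the 72 hour NO protocol".

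No section defines a within-patient difference, an SD of the change, a confidence interval or a repeated-measures model for mechanics. Nor does any section say whether the summaries are per visit or of the change, which of a session's several values enter, or whether the arms are pooled.

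**The concern.** The quantity named in the first purpose is a change within patients. The stated output is a mean, SD and range of something not specified. The natural reading is a table with one column per visit. Such a table shows how much patients vary at each visit. It does not show how much they vary in their change, and only the latter tells a reader how precisely the mean change is known.

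At stake is whether the report can say how far compliance, resistance, Vd/Vt or FRC moved over three days, and with what uncertainty. A shift of 0.3 SD, for example, could be well determined or compatible with no change, and two visit SDs would not tell the reader which.

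A related gap affects the PEEP titration. Item 5 ends a patient's PEEP trial if hypotension develops, so later steps may be measured in fewer patients than earlier ones. Means taken step by step would then be averages over different groups.

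**Working it through.** **The plan's own figures.** The plan gives no sample-size or precision figure for mechanics. Its only such figures belong to the primary endpoint: "Group sample sizes of 19 in group one and 19 in group two achieve 82% power", where the treatment proportion "is assumed to be 0.10 under the null hypothesis and 0.50 under the alternative hypothesis" and the control proportion is 0.10. Exact binomial enumeration of the two-sided pooled Z test with 19 per arm gives power 81.5% (stated 82%) and significance level 0.0361 (stated 0.0361). Both reproduce, and neither bears on mechanics.

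**Inputs for mechanics.**
- n = 38 pairs pooled, or 19 per arm (section 12). These are the evaluable numbers for the primary endpoint, taken here as the number of pairs.
- SD at each visit: not in the documents. Assumed equal at the two visits and used as the unit.
- r, the correlation between a patient's two values: not in the documents. Shown from 0 to 0.9.

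**Formula.** For values Y1 and Y2 in the same patient, Var(Y2 − Y1) = SD1² + SD2² − 2·r·SD1·SD2. With equal SDs, the SD of the change is SD·√(2(1 − r)). The 95% CI half-width for the mean change is t(0.975, n − 1)·√(2(1 − r))/√n, in SD units.

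**Numbers in.** For n = 38, t(37) = 2.026 and √38 = 6.164.
- r = 0: 2.026 × 1.414 / 6.164 = 0.465
- r = 0.9: 2.026 × 0.447 / 6.164 = 0.147

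| r | SD of change | Half-width, 38 pairs | Half-width, 19 pairs |
|---|---|---|---|
| 0 | 1.414 | 0.465 | 0.682 |
| 0.3 | 1.183 | 0.389 | 0.570 |
| 0.5 | 1.000 | 0.329 | 0.482 |
| 0.7 | 0.775 | 0.255 | 0.373 |
| 0.9 | 0.447 | 0.147 | 0.216 |

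The ratio of the extremes at 38 pairs is 0.465 / 0.147 = 3.2. Per-visit SDs alone therefore leave the width of the interval uncertain by about a factor of three.

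**If there are fewer pairs.** With 30 pairs (an illustrative number), the half-width runs from 0.167 at r = 0.9 to 0.528 at r = 0.

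**What per-visit summaries do give.** When the same patients are in both columns, mean(Y2) − mean(Y1) equals mean(Y2 − Y1). The point estimate can be had by subtraction. Its SD and interval cannot.

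**The case against.** The strongest reply has four parts.

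- **The plan does not exclude summarising change.** Mean, SD and range of each patient's change would satisfy the sentence in section 12. This stands. A reader might infer that the plan leaves the first purpose with no estimate at all. The documents do not support that: the sentence is silent on the point, and even per-visit means give the mean change by subtraction. What is missing is a specification of the change and of its precision.

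- **The two visits are largely the same patients.** A reader might infer that a Day 3 shift could not be told apart from a change in patient mix. The removal rule in section 12 largely answers this, because a patient extubated during the 72 hours leaves the analysis altogether. Death or a failed measurement could still cause some mismatch. The mix argument keeps its force only across PEEP steps, and the first purpose names time points, not PEEP steps.

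- **The gain from pairing depends on the correlation chosen.** A reader who treated the two visits as independent samples would get a half-width of t(74)·√(2/38) = 0.457 SD. Against that, pairing is 28% tighter at r = 0.5 (0.329) and 55% tighter at r = 0.8 (0.208). At r = 0.3 it is only 15% tighter (0.389), and at r = 0 there is no gain (0.465). No single percentage can be claimed from the documents.

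- **The aim is descriptive.** Section 6 says so, and the only stated hypothesis concerns oxygenation and dead space. The absence of a hypothesis test is therefore not an error. This too stands, but describing a change still calls for the change to be summarised with its precision.

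**Conclusion.** The point holds as a gap between the first stated purpose and the specified analysis. Section 12 defines neither the within-patient change nor an interval for it. If mechanics are reported per visit, the mean change can be obtained but its precision cannot: at 38 pooled pairs the 95% CI half-width lies anywhere from about 0.15 to 0.47 SD, and at 19 pairs from 0.22 to 0.68 SD. These figures assume equal SDs at the two visits, r between 0 and 0.9, and all evaluable patients contributing a pair.

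It does not affect the primary comparison, the sample size or the data to be collected. It is an inexpensive improvement to one of the study's two purposes, and should be made before the data are analysed.

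**What to change.** Keep the descriptive table and add the following to section 12.

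- **Paired change.** For compliance, resistance, Vd/Vt and FRC, report Day 3 minus session 1, using pre-gas values recorded at the same PEEP in both sessions. Give the mean change, SD of the change, 95% CI and number of pairs, and state how many patients have no matching PEEP level.
- **Pooled and by arm.** The pooled figure uses all pairs. The by-arm figures let the reader see whether the gas given in session 1 may have influenced the Day 3 pre-gas values.
- **Label.** State that the change applies to patients still ventilated at Day 3, as follows from item 7 of section 6 and the removal rule.
- **PEEP steps.** Because the titration can end early for hypotension, use within-patient contrasts between steps or a model with a patient effect, and give the number of patients at each step.

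A mixed model that also uses patients with session 1 data only should not be added as it stands. Extubated patients are the main such group, and section 12 removes them from the analysis, so the two would first have to be reconciled.

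The cost is a few lines in section 12 and routine analysis of data already being collected.
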